### **Randomization and masking**

A randomization sequence for 60 participants with an allocation ratio of 1:1 was generated using SPSS by an independent statistician who not involved in the clinical performance of the trial. The method of allocation concealment was sequentially numbered sealed opaque envelopes technique. Each participant got a study number at enrolment. An allocator (non-study personnel) then allocated participants to FMT or control group by the randomization sequence. This was done in a closed room and the allocation sequence were immediately disposed of. Investigators, patients and outcome assessors were kept masked to the allocation. The randomization key was revealed to researchers when all participants completed the 6-month follow-up and data analysis was completed.

### **Study duration**

The planned starting data of the study is December 2017, and the planned finishing data is December 2018.

### **Primary Endpoint**

The primary end point was the recovery of gastrointestinal dysfunction assessed by GIF score one week after intervention. The normal gastrointestinal function assessed by GIF score means enteral feeding >50% of calculated needs, without FI and IAH. FI was defined when applied enteral feeding appeared to be unsuccessful

and had to be discontinued because of repeated or profuse vomiting, high gastric residuals, ileus, severe diarrhea, abdominal pain, or distension. FI should not be considered as present if enteral feeding is electively not prescribed or is withheld/interrupted due to procedures. IAP was measured by the standardized methodology (preferably the transvesical method, with a maximal instillation of 25 cc of saline in the supine position, measured at the end of expiration, with zeroing done at the level of the midaxillary line). IAH was present if the IAP was found to be 12 mmHg or higher, as confirmed by at least two measurements taken 1-6 h apart.

### **Secondary endpoints**

The secondary end points were any infectious complication, OF, functional assessments of gut barrier and inflammatory indicators, hospital stay and mortality. Infectious complications included IPN, infected ascites, bacteremia, pneumonia, urinary tract infection. Microbiological data for each of the infectious complications were collected. OF was defined as a score of 2 or more using the modified Marshall scoring system, which was recommended by 2012 Atlanta Classification Creation. Persistent organ failure, that is, organ failure >48 hours. Blood samples were collected from all included patients before and one week after intervention. Gut barrier function was assessed by detecting serum D-Amino Acid Oxidase (DAO) and endotoxin using commercial kits (Cloud-Clone Corp, TX, USA for DAO and ELX800 (Bio Tek) for endotoxin). C-reactive protein (CRP) and procalcitonin (PCT) were measured by IMMAGE 800 (Beckman Coulter) and AFIAS-50 (JOINSTAR) separately. Stools were requested for microbiota analysis at baseline, one week and two week after intervention.

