### **Exclusion criteria**

- 1) Complicated by gastrointestinal bleeding or intestinal fistula;
- 2) Pregnancy and lactation women;
- 3) Not signed the informed consent;

- 4) Diabetes and autoimmune disease;
- 5) Multiple organ failure, which was defined as two or more organ failure including respiratory failure, renal failure or circulatory failure, which was defined as a score of 2 or more using the modified Marshall scoring system^17.

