## **Intervention**

All participants underwent interventions one day after allocation. In the FMT group,

participants received 200 mL fresh donor feces for twice (once every two days). In the control group, participants received 200 mL normal saline. The fecal transplant or normal saline were drawn on 50 mL sterile sealed syringe and infused into each patients via a nasoduodenal tube, which was inserted into distal duodenum by endoscopy. The procedure was performed within 5 min at the bedside of pancreatic intensive care unit by a researcher who were not involved in the clinical performance of the trial. The patients were blinded to the identity of the intervention that they were receiving because either FMT or placebo were stored on a sealed syringe. Before FMT or normal saline, Laxative was stopped for at least one hour to retain stool. To assure maximum delivery and colonization of these fecal transplant, first we assured a at least 4-hour gap between study medication and antibiotics (if prescribed) or laxative. No probiotics or lactulose was used during hospitalization. Considering the feasibility, we altered the protocol (after registration at ClinicalTrials.gov, but before enrolment of participants) to implement FMT or normal saline via a nasoduodenal tube instead of via retention enema.

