### **Follow up**

Patients are followed during their hospital stay. There is one follow-up visit, 6 months after discharge by clinical visit or telephone visit, to assess readmission, mortality and adverse events.

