### **Statistical analysis**

Quantitative variables are presented as medians (ranges) or means  $\pm$  standard deviations and were analysed using the Mann-Whitney U test or t-test as appropriate. Categorical variables are reported as absolute numbers and proportions and were tested by the chi-square test or Fisher's exact test as appropriate. The differences between outcomes for matching data were tested with the paired t test or Wilcoxon signed-rank test as appropriate. We estimated relative risks (RRs) and 95% confidence intervals (CIs) for primary outcomes and secondary outcomes. A two-tailed P value  $<0.05$  was considered statistically significant. Data were analyzed using SPSS software (v17.0; SPSS Inc., Chicago, IL, USA).

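### Does the missing start time for the organ-failure endpoint pull its relative risk toward 1?

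*Combined protocol and SAP*

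**What the plan says.** Secondary endpoints lists the outcomes: "The secondary end points were any infectious complication, OF, functional assessments of gut barrier and inflammatory indicators, hospital stay and mortality". It defines OF by a threshold alone: "OF was defined as a score of 2 or more using the modified Marshall scoring system". Persistent OF adds a duration of more than 48 hours, but no point from which those hours run. Other measures in the section are timed against treatment, for example "Blood samples were collected from all included patients before and one week after intervention"; OF is not.

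Exclusion criteria uses the same Marshall cut-off but removes only the multi-organ case: "Multiple organ failure, which was defined as two or more organ failure including respiratory failure, renal failure or circulatory failure". A single failed organ is therefore allowed at entry.

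Intervention places treatment after randomization: "All participants underwent interventions one day after allocation". Follow up says "Patients are followed during their hospital stay", and adds: "There is one follow-up visit, 6 months after discharge by clinical visit or telephone visit, to assess readmission, mortality and adverse events". Statistical analysis states the effect measure: "We estimated relative risks (RRs) and 95% confidence intervals (CIs) for primary outcomes and secondary outcomes". It has no rule for OF already present at entry.

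**The concern.** A patient with one failed organ satisfies the endpoint definition before receiving anything. If such patients are scored as events whatever happens later, similar numbers are added to both arms and the ratio of the two risks is compressed. The same applies to persistent OF, where the 48 hours could begin before the first infusion, and to failure arising in the day between allocation and infusion.

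The interpretation of the OF result would be at stake. One RR could describe any OF during the stay, OF status after treatment, or OF that is new since treatment. A reader could not tell prevention from resolution, and a choice left open until analysis leaves room to pick among versions. Single-organ failure at entry is plausible: patients come from an ICU and may be up to two weeks from onset.

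**Working it through.** The plan gives no OF rate and no prevalence of OF at entry, so it has no figure of its own to reproduce here. Its sample size rests on the primary endpoint only. From the plan: 30 patients per arm, RR with 95% CI. Assumed for illustration: q, the share with single-organ OF at entry; new OF in the other patients, 30% control and 15% FMT (RR 0.50).

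**1. Every entry case counted.** RR = [q + (1 − q) × 0.15] / [q + (1 − q) × 0.30].
- q = 0.10: 0.235 / 0.370 = 0.635
- q = 0.20: 0.320 / 0.440 = 0.727

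With 10% v 20% the results are 0.679 and 0.778; with 20% v 40%, 0.609 and 0.692.

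**2. OF status after treatment.** Let half of entry OF remain in control and a share r remain with FMT. RR = [q × r + (1 − q) × 0.15] / [q × 0.5 + (1 − q) × 0.30]. At q = 0.20 the denominator is 0.10 + 0.24 = 0.34.
- r = 0.50: 0.220 / 0.34 = 0.647
- r = 0.375: 0.195 / 0.34 = 0.574
- r = 0.25: 0.170 / 0.34 = 0.500, no shift

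**3. Absolute scale, q = 0.20.** Entry cases counted: 44% − 32% = 12 points. New OF only, with no further organ failure in patients who entered with OF: 0.8 × 30% − 0.8 × 15% = 24% − 12% = 12 points. The compression belongs to the ratio scale.

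**4. No effect.** If new OF has the same risk p in both arms, both totals are q + (1 − q)p and the expected risks are equal. Counting entry cases does not create a false difference in expectation.

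**5. Precision, q = 0.20, 30 per arm.** Wald interval on log RR, SE = √(1/a − 1/30 + 1/c − 1/30), where a and c are the expected events.

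| Definition | Events, FMT v control | SE | RR (95% CI) |
|---|---|---|---|
| Entry cases counted | 9.6 v 13.2 | 0.337 | 0.73 (0.38 to 1.41) |
| New OF, no further failure in entry cases | 3.6 v 7.2 | 0.592 | 0.50 (0.16 to 1.59) |
| New OF, entry cases fail in a second organ at the same rate as others | 4.5 v 9.0 | 0.516 | 0.50 (0.18 to 1.38) |

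Power by exact enumeration (Fisher's test if an expected count is below 5, otherwise chi-square), in the table's order: 15.5%, 19.0% and 27.2% at q = 0.20; 11.0%, 10.5% and 27.2% at q = 0.40. All are low.

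**6. Chance.** At q = 0.40, with new OF at 20% v 40%, an even 12 v 12 split of entry cases gives 0.52 / 0.64 = 0.81. The SD of the difference in entry cases is √(2 × 30 × 0.4 × 0.6) = 3.8, so a gap of 6 is about 1.6 SD. FMT 9 v control 15 gives 0.44 / 0.70 = 0.63; 15 v 9 gives 0.60 / 0.58 = 1.03. In simulations with a new-onset RR of 0.50 (q from 20% to 60%), adding entry cases brought the observed RR nearer 1 in about 83% to 93% of trials: a tendency, not a rule.

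**The case for a change.** The strongest case for a change is that the gap is real and nothing else in the document closes it. Entry at the same cut-off is allowed, the effect measure is a ratio, and the remedy looks cheap: define OF as new failure after the first infusion, in an organ system below the cut-off beforehand, keep everyone randomized in the denominator, and report resolution of entry OF separately. Marshall scores at entry are already needed for the exclusion.

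The textual part stands, for persistent OF as well. The step to a required correction does not. Counting every entry case is one reading, not the plan's stated rule; OF is listed as an outcome of treatment and patients are followed through the stay, which fits status after treatment just as well. New OF is a different question. The primary endpoint here is recovery, and under a new-OF rule a patient whose entry failure never resolves would count as a non-event. In the illustration the interval widens from 0.38–1.41 to 0.16–1.59, and power may rise or fall with inputs nobody has. The worry about choosing among versions is eased by Randomization and masking, which keeps the key from the researchers until data analysis is complete. A table of entry OF by arm and a note on when infections count are reporting details.

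**Conclusion.** The assessment window for OF is unwritten, but the plan is not shown to be wrong. The move toward 1 needs three things: that entry cases are counted, that they do not resolve in proportion to the effect on new OF, and that the arms are reasonably balanced at entry. If all hold, an RR of 0.50 would read about 0.64 to 0.73 with 10% to 20% of patients in OF at entry, on rates that are wholly assumed; with few such patients the shift is negligible. The absolute difference is the same in the worked case, a null effect stays null in expectation, and the primary endpoint and sample size are untouched. Analysts can fill this gap by stating in the report which OF they counted and showing entry status by arm. Choosing new OF over status after treatment is a matter on which competent statisticians would differ, and it brings no assured gain. No change to the plan follows.

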### **Microbiomics analysis**

Fecal samples were longitudinally collected from patients at baseline before first FMT, one weeks and two weeks after first FMT. The fresh feces were collected in sterile cryopreservation tube by the nurses and kept at -20 °C immediately. Then, the feces were transferred within 6 hour after a bowel movement, and were stored at -80 °C until DNA extraction.

Bacterial DNA was extracted from fecal samples using the E.Z.N.A. Soil DNA Kit (Omega Bio-Tek, Norcross, GA, USA) according to the manufacturer's instructions. The final DNA concentration and purification were determined by NanoDrop 2000 UV-vis spectrophotometer (Thermo Scientific, Wilmington, USA), and DNA quality was checked by 1% agarose gel electrophoresis. The V3-V4 hypervariable regions of the bacteria 16S rRNA gene were amplified with primers 338F (5'-ACTCCTACGGGAGGCAGCAG-3') and 806R (5'-GGACTACHVGGGTWTCTAAT-3') by thermocycler PCR system (GeneAmp 9700, ABI, USA). The PCR reactions were conducted using the following program: 3 min of denaturation at 95°C, 27 cycles of 30 s at 95°C, 30 s for annealing at 55°C, and 45 s for elongation at 72°C, and a final extension at 72°C for 10 min. PCR reactions were performed in triplicate 20 µL mixture containing 4 µL of 5 × FastPfu Buffer, 2 µL of 2.5 mM dNTPs, 0.8 µL of each primer (5 µM), 0.4 µL of FastPfu Polymerase and 10 ng of template DNA. The resulted PCR products were extracted from a 2% agarose gel and further purified using the AxyPrep DNA Gel Extraction Kit (Axygen Biosciences, Union City, CA, USA) and qualified using QuantiFluro-ST (Promega, USA).

Purified amplicons were pooled in equimolar and paired-end sequenced (2×300) on an Illumina MiSeq platform (Illumina, San Diego, USA). The raw reads were deposited into the NCBI Sequence Read Archive (SRA) database (Accession Number: SRP). The raw reads were demultiplexed and quality-filtered by Trimmomatic and merged by FLASH software. The high-quality sequences were assigned to samples according to barcodes. Operational taxonomic units (OTUs) were clustered with 97% similarity cutoff using UPARSE (version 7.1, <http://drive5.com/uparse/>) and chimeric sequences were identified and removed using UCHIME. The taxonomy of each 16S rRNA gene sequencing was analyzed by RDP Classifier algorithm (<http://rdp.cme.msu.edu/>) against the Siva (SSU123) 16S rRNA database using confidence threshold of 70%.

## **Intervention**

All participants underwent interventions one day after allocation. In the FMT group,

participants received 200 mL fresh donor feces for twice (once every two days). In the control group, participants received 200 mL normal saline. The fecal transplant or normal saline were drawn on 50 mL sterile sealed syringe and infused into each patients via a nasoduodenal tube, which was inserted into distal duodenum by endoscopy. The procedure was performed within 5 min at the bedside of pancreatic intensive care unit by a researcher who were not involved in the clinical performance of the trial. The patients were blinded to the identity of the intervention that they were receiving because either FMT or placebo were stored on a sealed syringe. Before FMT or normal saline, Laxative was stopped for at least one hour to retain stool. To assure maximum delivery and colonization of these fecal transplant, first we assured a at least 4-hour gap between study medication and antibiotics (if prescribed) or laxative. No probiotics or lactulose was used during hospitalization. Considering the feasibility, we altered the protocol (after registration at ClinicalTrials.gov, but before enrolment of participants) to implement FMT or normal saline via a nasoduodenal tube instead of via retention enema.

### **General treatment regimen**

All participants received routine treatment at admission according to the AP guidelines, including goal-oriented fluid resuscitation, enteral nutrition as early as possible, organ support as needed. Antibiotic prophylaxis was not given routinely. The use of antibiotics was recorded, irrespective of indication. As all the patients enrolled was complicated with gastrointestinal failure, we used traditional Chinese medicine-rhubarb (and/or mirabilite) for all patients. Some other purge measures including gastrointestinal decompression or mannitol via nasoduodenal tube were conducted according to patients' conditions. Abdominal puncture and drainage were for patients with abdominal effusion.

### **Data collection**

Data collection was prospectively entered by a researcher, who completed standardized case report forms. During the study an independent data monitor checked the individual patients' data against the primary source data. After double check of key variables by two researchers, data were exported unedited for statistical

analyses.

### **Follow up**

Patients are followed during their hospital stay. There is one follow-up visit, 6 months after discharge by clinical visit or telephone visit, to assess readmission, mortality and adverse events.

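### Infection, organ failure and mortality have no fixed assessment day from randomisation, and follow-up is tied to discharge, so a difference in hospital stay could bias the infection relative risk.

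*Combined protocol and SAP*

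**What the plan says.** All references are to the combined protocol and SAP.

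- **Secondary endpoints:** "The secondary end points were any infectious complication, OF, functional assessments of gut barrier and inflammatory indicators, hospital stay and mortality". The infection endpoint is then defined by type: "Infectious complications included IPN, infected ascites, bacteremia, pneumonia, urinary tract infection". No start or end day is given for infection, organ failure or mortality.
- **Follow up:** "Patients are followed during their hospital stay". After that, "There is one follow-up visit, 6 months after discharge by clinical visit or telephone visit, to assess readmission, mortality and adverse events". Infections are not on that list, and the contact is timed from discharge.
- **Randomization and masking:** "The randomization key was revealed to researchers when all participants completed the 6-month follow-up and data analysis was completed". This section does not say from when the 6 months run.
- **Statistical analysis:** categorical outcomes "were tested by the chi-square test or Fisher's exact test as appropriate", and "We estimated relative risks (RRs) and 95% confidence intervals (CIs) for primary outcomes and secondary outcomes". There is no time-to-event, person-time or competing-risk method.

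Other assessments do have times. The primary endpoint and the blood samples are set at one week after intervention, and stool is sampled at baseline, one week and two weeks.

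**The concern.** Scheduled observation for infection lasts as long as the hospital stay. Discharge happens after randomisation, and hospital stay is itself a secondary endpoint, so treatment could affect the length of the window. Faster gut recovery, which is what the trial hopes to show, could shorten stay without changing the risk of infection. A crude RR would then compare unequal observation times.

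The Introduction names infectious complications among the things the trial sets out to clarify, so this is a prominent secondary comparison. An open window also leaves the counting rule to be chosen later. Mortality has a related ambiguity: it could mean death in hospital or death by the late contact, and neither is a fixed day from randomisation.

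**Working it through.** **Inputs.** The documents give no infection rate, no expected stay and no figure of their own for this point, so there is nothing to reproduce. Everything below is assumed, except the 30 patients per arm from the Sample size section.

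- Infection hazard *h* while in hospital, the same in both arms: 1%, 2% or 3% per day. Treatment therefore has no effect on the daily risk in hospital.
- Stay from randomisation: 14 days in one arm, 20 in the other. The RR is the shorter-stay arm over the longer-stay arm.
- After discharge the hazard is *k* × *h*, with *k* between 0 and 1.
- No deaths, and stay does not depend on infection. Both are simplifications.

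**Step 1: only in-hospital infections counted.** Risk = 1 − exp(−*h* × days in hospital).

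| *h* per day | 14 days | 20 days | RR |
|---|---|---|---|
| 1% | 13.1% | 18.1% | 0.72 |
| 2% | 24.4% | 33.0% | 0.74 |
| 3% | 34.3% | 45.1% | 0.76 |

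At 2% per day: 1 − exp(−0.28) = 0.244, 1 − exp(−0.40) = 0.330, and 0.244 / 0.330 = 0.74. With stays of 17 and 20 days the RR is 0.86 to 0.89. With equal stays it is 1.

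**Step 2: all infections to day 28 counted.** Risk = 1 − exp(−*h* × stay − *k* × *h* × (28 − stay)).

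| Hazard after discharge | RR at 1% | RR at 2% | RR at 3% |
|---|---|---|---|
| unchanged (*k* = 1) | 1.00 | 1.00 | 1.00 |
| half (*k* = 0.5) | 0.89 | 0.90 | 0.91 |
| quarter (*k* = 0.25) | 0.81 | 0.83 | 0.85 |
| tenth (*k* = 0.1) | 0.76 | 0.78 | 0.80 |
| none (*k* = 0) | 0.72 | 0.74 | 0.76 |

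Example, *k* = 0.5 at 2%: shorter-stay arm 1 − exp(−0.28 − 0.14) = 0.343; longer-stay arm 1 − exp(−0.40 − 0.08) = 0.381; ratio 0.90. With *k* = 1 the day-28 risk at 2% is 1 − exp(−0.56) = 42.9% in both arms.

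The distortion is the gap between the two tables. It is largest when the hazard carries on unchanged after discharge, small at *k* = 0.1 and nil at *k* = 0.

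**Step 3: effect on the test.** With 30 per arm and true in-hospital proportions of 24.4% and 33.0%, the difference reaches P < 0.05 in about 7% of trials with Fisher's exact test and about 11% with the uncorrected chi-square test, against a nominal 5%.

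**Step 4: timing of the late contact.** Taking 6 months as 180 days, the contact falls at day 14 + 180 = 194 in one arm and day 20 + 180 = 200 in the other. The gap is 6 days in about 200.

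**The case against.** A reader might infer that infections are counted only in hospital, and that the arm with shorter stays will therefore show fewer of them. The documents do not support either step.

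- **No counting rule is stated.** The late contact covers readmission and adverse events, and an infection after discharge could be recorded as either. The window is undefined, not expressly closed at discharge. This objection stands. It does not settle the matter, because nothing says that such events count toward the infection endpoint. The endpoint also calls for microbiological data on each infection, which a telephone call alone would not supply.
- **The bias is conditional.** Stays must differ between arms, infections must occur after discharge, and these must be missed. The plan lists hospital stay as an endpoint but states no expected difference. Infection can also prolong stay, and early death shortens observation, so the direction cannot be fixed in advance. This stands.
- **The RR is not meaningless.** If a shorter stay reduces exposure to hospital infection, part of a lower count is a real consequence of assignment. The rows with *k* below 1 show this: the day-28 RR is itself below 1. If infections arise almost entirely in hospital, a fixed window gives nearly the same answer.
- **The reach is limited.** The primary endpoint is set at one week after intervention and is unaffected. The discharge anchor moves the late contact by only a few days. For mortality the main problem is an unclear definition, and no bias in it has been shown.

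**Conclusion.** The concern holds in conditional form. The plan sets no common window from randomisation for infection, organ failure or mortality, ties observation to a post-randomisation event that is itself an endpoint, and analyses crude proportions. If infections are in practice counted only in hospital and stays differ, the infection RR could be biased in either direction.

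On the assumed inputs, the in-hospital RR of 0.72 to 0.76 compares with a day-28 RR anywhere from 1.0 down to the same 0.72 to 0.76, depending on how much infection risk remains after discharge. These figures show a mechanism and its range. They do not estimate what happened in this trial. The point concerns secondary endpoints and should be corrected, but it does not threaten the primary result.

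**What to change.** 1. Count new infections, new organ failure and deaths from randomisation to fixed days common to both arms: for example day 28 or later for infection and organ failure, and day 180 for death and readmission.
2. Time the single late contact from randomisation, and state which deaths the mortality endpoint includes.
3. Add a question at that contact on infections after discharge, checked against readmission records, and state that confirmed events count toward the endpoint if they fall within its window.
4. Report deaths alongside infection as a competing event.
5. Keep the in-hospital infection count as a descriptive result.

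The cost is revised endpoint wording, a changed anchor for one planned contact and one added question. The small downside is that infections after discharge rely on records or telephone report and may lack microbiological data.
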